7.7. EXAMINATION OF SUBGROUPS

Subgroup analyses will be conducted as supplementary analyses for the primary and key secondary efficacy endpoints as stated in Sections 16.1.5 and 16.2.5, respectively.

The subgroups are:

- Age (years) at informed consent ($\geq 18 - \leq 49$, $\geq 50 - \leq 64$; $\geq 65 - \leq 84$ or ≥ 85);
- Sex (male or female);
- Race (White, Black or African American or Other);
- Ethnicity (Hispanic or Latino or not Hispanic or Latino);
- Country (or region; refer to Section 7.5);
- Obesity co-morbidity at screening ($BMI < 30 \text{ kg/m}^2$ or $BMI \geq 30 \text{ kg/m}^2$);
- Diabetes co-morbidity at screening (yes or no);
- Cardiovascular disease co-morbidity at screening (yes or no);
- Hypertension co-morbidity at screening (yes or no);

CCI

PPD

Version Number: Amendment 1, v1.0
Version Date: 23Apr2021

CCI

Master Statistical Analysis Plan

- Chronic lung disease co-morbidity at screening (yes or no);
- Chronic liver disease co-morbidity at screening (yes or no);
- Kidney disease co-morbidity at screening (yes or no);
- Immunosuppressive/Immunocompromise disorder co-morbidity at screening (yes or no);
- Time since hospital admission (≤ 5 days or > 5 days; refer to Section 11.1);
- Baseline clinical severity score of 2 randomization strata (yes or no) as captured on the IWRS;
- Disease severity at baseline (2, 3, 4, or 5) based on the ordinal scale for clinical severity as captured on the *Ordinal Scale for Clinical Severity* page on the eCRF;
- Disease severity score of 2, 3 or 4 (yes or no) at baseline based on the ordinal scale for clinical severity as captured on the *Ordinal Scale for Clinical Severity* page on the eCRF
- Remdesivir use at baseline randomization strata (yes or no) as captured on the IWRS;
- Concomitant use of remdesivir at any time during the period of the endpoint of interest (yes or no) based on collected on the *Concomitant Medications* page of the eCRF (for concomitant use definition, refer to Section 13). The concomitant use of remdesivir at any time during the period of the endpoint of interest in the ‘yes’ subgroup will be further broken down by duration of concomitant use of remdesivir, where the duration of concomitant use categories (e.g., $< x$ days or $\geq x$ days) will be determined in a blinded fashion based on emerging data before the interim database lock of a candidate agent primary analysis;
- Dexamethasone use at baseline (yes or no) based on data collected on the *Concomitant Medications* page of the eCRF (i.e., medications that were being taken by a patient on the day the patient was randomized to a sub-protocol);
- Concomitant use of dexamethasone at any time during the period of the endpoint of interest (yes or no) based on data collected on the *Concomitant Medications* page of the eCRF (for concomitant use definition, refer to Section 13). The concomitantly use dexamethasone at any time during the period of the endpoint of interest ‘yes’ subgroup will be further broken down by duration of concomitant use of dexamethasone, where the duration of concomitant use categories (e.g., $< x$ days or $\geq x$ days) will be determined in a blinded fashion based on emerging data before the interim database lock of a candidate agent primary analysis.

For age subgroups, if data are too sparse for the ‘ $\geq 18 - \leq 49$ ’ or ‘ $\geq 50 - \leq 64$ ’ subgroups (i.e., less than 10% of FAS

CCI

PPD

Version Number: Amendment 1, v1.0
Version Date: 23Apr2021

CCI

patients, regardless of the treatment arm), these two subgroups will be pooled together into a ' $\geq 18 - \leq 64$ ' subgroup. Similarly, if data are too sparse for the ' $\geq 65 - \leq 84$ or ' ≥ 85 ' subgroups, these two subgroups will be pooled together in a ' ≥ 65 ' subgroup. If even after pooled two subgroups, the resulting ' $\geq 18 - \leq 64$ ' or ' ≥ 65 ' subgroup is still less than 10% of FAS patients, regardless of the treatment arm, only descriptive statistics will be provided for the concerned subgroup.

For race subgroups, if data are too sparse for the 'Black or African American' or 'Other' subgroups (i.e., less than 10% of FAS patients, regardless of the treatment arm), the 'Black or African American' and 'Other' subgroups will be pooled together into a 'Non-White' subgroup. If even after having pooled these two subgroups the number of patients in the resulting 'Non-White' subgroup is still less than 10% of FAS patients, regardless of the treatment arm, only descriptive statistics will be provided for the 'Non-White' subgroup.

For the disease severity at baseline subgroups, if data are too sparse for the subgroups of patients with a disease severity at baseline of 3 or 4 (i.e., less than 10% of FAS patients, regardless of the treatment arm), these two subgroups will be pooled together. If data are too sparse for the subgroup of patients with a disease severity at baseline of 2, pooled 3/4 (if applicable) or 5, only descriptive statistics will be provided for the concerned subgroups. That is, the subgroup of patients with a disease severity at baseline of 2 or 5 will not be pooled with any other subgroup.

For any other subgroups, if data are too sparse (i.e., less than 10% of FAS patients for a subgroup, regardless of the treatment arm), only descriptive statistics will be provided for the concerned subgroups.

Additional subgroups might be defined based on emerging data to explore the impact of medical therapy in COVID-19 with proven efficacy (e.g., vaccine use, other evolving SoC, etc.). The decision to add such subgroups and their definition will be taken in a blinded fashion before the interim database lock of a candidate agent primary analysis based on data captured on the *Concomitant Medications* page of the eCRF.

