7.1. SAMPLE SIZE CALCULATION

A total of up to 350 patients are planned to be randomized to each candidate agent plus SoC. Simultaneously, patients will be randomized to placebo plus SoC throughout the course of the study. The subset of shared placebo

CCI

PPD

Version Number: Amendment 1, v1.0
Version Date: 23Apr2021

CCI

plus SoC treatment arm, regardless of which sub-protocol the placebo belongs, enrolled concurrently to an active agent with matching inclusion/exclusion criteria will serve as comparator (refer to Section 4.5). The primary efficacy endpoint to compare selected treatment plus SoC to placebo plus SoC included in the control arm will be the time to confirmed clinical recovery through Day 29 i.e., fit for discharged (defined by achieving a score of 6, 7 or 8 on the 8-point ordinal scale for clinical severity status), without re-hospitalization through Day 29 (refer to Section 16.1.1).

Assuming a median time to confirmed clinical recovery of 11 days for patients randomized to a candidate agent plus SoC arm compared with 15 days for those randomized to its concurrent placebo plus SoC arm, 350 patients are needed per arm in order to observe 490 confirmed clinical recovery events between the 2 treatment arms being compared at the primary analysis of a sub-protocol. This sample size will provide approximately 88% power to detect a hazard ratio (HR) of 1.364 for the occurrence of the confirmed clinical recovery events, when comparing each candidate agent plus SoC with their concurrent placebo plus SoC arm, at a one-sided significance level of 0.025.

This sample size will provide the following information about the key secondary efficacy endpoints:

- Assuming the oxygen-free recovery rate at Day 29 is 65% for the concurrent placebo plus SoC arm of a candidate agent, a sample size of 350 patients per arm will provide approximately 80% power to detect a 9.7% absolute increase in the proportion of patients who have oxygen-free recovery at Day 29 in the candidate agent plus SoC arm;
- Assuming 70% of patients randomized to the concurrent placebo plus SoC arm of a candidate agent achieve at least 2-point improvement from baseline on the 8-point ordinal scale or are fit for discharge at Day 29, 350 patients per arm will provide approximately 80% power to detect a 9.2% absolute increase in this proportion with a candidate agent plus SoC arm at Day 29;

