16.1.5. SUPPLEMENTARY ANALYSES FOR PRIMARY EFFICACY ENDPOINT

The following supplementary analyses to the main analysis of the primary efficacy endpoint will be performed:

- The main analysis to the primary efficacy endpoint will be repeated (refer to Section 16.1.3) but without country (region; refer to Section 7.5) included as stratification variable;
- The main analysis of the primary efficacy endpoint will be repeated but without the requirement for follow-up confirmation. That is, for this analysis, patients will be considered as having met the event as soon as they reach a score of 6, 7 or 8 on the 8-point ordinal scale, regardless of if they subsequently worsened or were re-hospitalized before or on Day 29, exception of patients with a score of 7 discharged to hospice care who will

still be considered as not having the event;

- The main analysis of the primary efficacy endpoint will be repeated for each subgroup defined in Section 7.7. For subgroups corresponding to one of the factors included in the main model, the corresponding factor will be excluded from the model. For example, the remdesivir use at baseline (yes/no) stratification variable as captured on the IWRS will not be included in the model for the analysis of the patients who received remdesivir at randomization as captured on the IWRS subgroup, and analysis of the patients who did not receive remdesivir at randomization as captured on the IWRS subgroup.

[figure not shown]

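### Subgroups formed by remdesivir or dexamethasone use during follow-up, and by its duration, give distorted hazard ratios when the agent changes recovery

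*SAP*

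**What the plan says.** Master SAP Section 7.7 lists a subgroup by "Concomitant use of remdesivir at any time during the period of the endpoint of interest (yes or no". Its users' group "will be further broken down by duration of concomitant use of remdesivir", at a cut-off to be chosen blinded from emerging data. Dexamethasone is handled in the same way: "Concomitant use of dexamethasone at any time during the period of the endpoint of interest (yes or no", then by duration. Section 13 counts as concomitant any drug started on or after Study Day 1.

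For the primary endpoint, Section 16.1.5 states: "The main analysis of the primary efficacy endpoint will be repeated for each subgroup defined in Section 7.7". That means the stratified log-rank test and the Cox HR. Section 16.2.5 does the same for the key secondary logistic models. None of these sections gives a landmark rule, a time-dependent method or a caution on interpretation.

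Section 7.7 also lists subgroups by remdesivir and dexamethasone use at baseline, calls all subgroup analyses supplementary, and closes by allowing further subgroups built from concomitant-medication data.

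**The concern.** A subgroup comparison keeps the protection of randomization only if membership is fixed before treatment can act. Here it is fixed afterwards, during the 29 days in which recovery is counted. If a background drug is given in hospital and stops at recovery or discharge, short use is largely a result of fast recovery, and a patient who recovers early has less time to start the drug at all. An agent that speeds recovery therefore changes who falls in each group, and the arms within a group are no longer comparable. A blinded choice of the duration cut-off does not help, because the fault lies in conditioning on the outcome and not in how the cut is picked.

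At stake is the reading of results by background therapy for an agent that works, which is when such results would be consulted. The bias is systematic, so a larger sample does not remove it.

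**Working it through.** **Inputs from the documents.** Section 7.1 assumes "a median time to confirmed clinical recovery of 11 days for patients" on the candidate agent, "compared with 15 days for those randomized to its concurrent placebo", so the HR is 15/11 = 1.364. It plans 350 patients per arm and 490 events. Follow-up for the primary endpoint ends at Day 29.

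**Check of the plan's own figure.** Section 7.1 claims "approximately 88% power to detect a hazard ratio (HR) of 1.364" "at a one-sided significance level of 0.025". For a fixed design, z = √(490/4) × ln(1.364) − 1.96 = 11.07 × 0.3104 − 1.96 = 1.476, which is 93.0% power. Adding the looks at 123 and 270 events with futility p-values 0.503 and 0.175 (z = −0.008 and 0.935), and counting a crossing as failure, gives 88.3%. The null stopping probabilities are 49.7% and 34.6%. All three match Section 16.5.1, so the inputs are read as intended.

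**Mechanism, short use.** Suppose recovery times are exponential and every patient is on the drug from Day 1 and stops early only on recovery. Then use of under 5 days means recovery before 5 days:
- placebo: 1 − 2^(−5/15) = 20.6% of patients
- active: 1 − 2^(−5/11) = 27.0% of patients

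Everyone in this group has the event, in both arms. Only the order of events within 5 days is left to compare, and the simulated HR is about 1.02.

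**Mechanism, non-users.** The daily recovery hazards are ln 2/15 = 0.0462 and ln 2/11 = 0.0630. If patients still ill start the drug at rate λ, those never treated are mostly those who recover first. Well before Day 29 their hazard is close to the recovery hazard plus λ. With λ = 0.05 the ratio is (0.0630 + 0.05)/(0.0462 + 0.05) = 0.1130/0.0962 = 1.17. It rises towards 1.364 as Day 29 nears, so the fitted HR lies between the two.

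**Simulation.** The documents give no use rates, so these are assumptions: 0 to 70% on the drug at baseline, later starts at 3 to 10% per day while ill, a 5- or 10-day course ending early on recovery, a cut at 5 or 7 days, and the same prescribing rule in both arms. Cox HRs come from several hundred thousand simulated patients per setting. Selected results (10-day course; 7-day cut unless stated):

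| Setting | Users | Non-users | Short | Long |
|---|---|---|---|---|
| True HR 1.364; 0% at baseline; 3, 5, 10% per day | 1.42, 1.40, 1.39 | 1.30, 1.26, 1.17 | – | – |
| True HR 1.364; 30%; 3% per day | 1.40 | 1.29 | 1.24 | 1.39 |
| True HR 1.364; 50%; 5% per day | 1.39 | 1.26 | 1.18 | 1.38 |
| True HR 1.364; 50%; 10% per day | 1.38 | 1.16 | 1.14 | 1.38 |
| True HR 1.364; 70%; 3% per day | 1.39 | 1.30 | 1.13 | 1.38 |
| True HR 1.364; 100% at baseline; 5-day cut | – | – | 1.02 | 1.36 |
| True HR 1.0; 50%; 5% per day | 1.00 | 1.00 | 1.01 | 1.00 |

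In the 50% and 5% per day setting, 74% of placebo and 71% of active patients become users, so the grouping itself responds to treatment. With patient-to-patient variation in prognosis added (log-hazard SD 0.8, overall HR about 1.27), the HRs are 1.29 against 1.22 by use, and 1.14 to 1.15 (short) against 1.24 to 1.25 (long).

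**Comparison with baseline subgroups.** With membership fixed at baseline, the HR is 1.36 to 1.38 in users and non-users alike. In trials of 350 per arm with a true HR of 1.364, a nominal 5% interaction test rejects in 4.4 to 5.3% of trials for baseline use, 7 to 14% for any use during follow-up, and 8 to 16% for duration.

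**The case against.** The strongest reply is that little depends on these outputs. They are supplementary and outside the testing hierarchy, and the SAP plans no interaction test for them. Subgroups with under 10% of patients get descriptive statistics only, and clean baseline versions are already planned. The lanadelumab and zilucoplan SAPs (Section 7.7 of each) have dropped subgroup analyses. All of this stands and limits the impact. It does not make the estimates correct: the apremilast SAP (Section 16) still takes its efficacy analyses from the Master SAP.

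The size is also open to challenge. If 30% of planned courses are shorter for unrelated reasons, the duration contrast shrinks to 1.32 against 1.39. The interaction test would flag the bias in only a minority of trials.

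A reader might infer three stronger things that the documents do not support:
- **That these subgroups will always show false differences.** With a true HR of 1.0 and equal prescribing, every subgroup HR is 0.99 to 1.01 and the interaction test rejects in 4.4 to 5.8% of trials.
- **That the agent would appear to work only in users or only with long background therapy.** This needs an HR near 1 in the other group. It arises only in the extreme case of 100% baseline use with recovery as the sole reason for stopping early. Under mixed use the smaller HR stays above 1, in the direction of the overall effect.
- **That labelling would follow.** Nothing in the documents says so.

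**Conclusion.** The point holds as a bias in supplementary estimates, conditional on the agent changing recovery and on in-hospital use ending at recovery or discharge. With the same true HR of 1.364 in everyone, the mixed-use settings give about 1.37 to 1.42 in users against 1.16 to 1.30 in non-users, and about 1.13 to 1.30 for short against 1.37 to 1.41 for long use. Combinations not run can fall slightly outside these ranges. The short-use HR falls to about 1.02 only in the extreme case.

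These sizes rest on assumed use rates, exponential recovery and equal prescribing by arm; deaths and withdrawals were not modelled. The bias in the Day 29 binary endpoints has not been computed. The primary and key secondary tests, alpha and power are unaffected. The change is worth making because the stated rule gives misleading estimates when the agent works and sound alternatives are already in the SAP.

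**What to change.** - Remove the subgroups by use at any time during the endpoint period, and by duration of that use, from the treatment-effect analyses in Master SAP 7.7, 16.1.5 and 16.2.5, for both drugs.
- Rely on the baseline remdesivir and dexamethasone subgroups already listed.
- Report later use by arm descriptively in Section 13. That section now covers yes/no use but not duration, so add duration, and update its references to 7.7.
- Limit the additional subgroups allowed at the end of 7.7 to baseline or pre-randomization status.
- If an effect by later use is wanted, specify a landmark or time-dependent analysis.

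The cost is SAP wording and fewer effect outputs. The downside is that effect estimates by follow-up use are no longer produced.

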7.8. SOFTWARE VERSION

All analyses will be conducted using SAS version 9.4.

8. OUTPUT PRESENTATIONS

[figure not shown]
[Appendix 2](#) shows conventions for presentation of data in outputs.

CCI

PPD

Version Number: Amendment 1, v1.0
Version Date: 23Apr2021

CCI

The table, figure, and listing (TFL) shells provided with this SAP describe the presentations for each sub-protocol in accordance with this master SAP and therefore, the format and content of the summary tables, figures, and listings to be provided by CCI Biostatistics. If a sub-protocol has additional endpoints or analyses, additional TFL shells will be provided with the sub-protocol SAP.

9. DISPOSITION AND WITHDRAWALS

All patients who provide informed consent will be accounted for in this study.

9.1. DISPOSITION

Number and percentages of patients treated, ongoing on study drug, who completed/ discontinued early from treatment (including reason for withdrawal), ongoing in study, and who completed/discontinued early from the study (including reason for withdrawal) will be provided overall and by treatment arm based on the FAS. The control arm of a candidate agent (refer to Section 4.5) will be further broken down by sub-protocol. It is to be noted that the number and percentage of patients ongoing on study drug and ongoing in study will be excluded from the summary at the time of the final analysis.

In addition, a Kaplan-Meier curve (product-limit estimate) of time to discontinuation from study, in days, for each treatment arm will be provided along with a summary of the associated statistics including, the 25th, 50th (median), and 75th percentiles, and their corresponding two-sided 95% CIs. The control arm of a candidate agent (refer to Section 4.5) will be further broken down by sub-protocol. Patients who are ongoing in the study at the time of an analysis will be censored at the date of the last contact before or on the date of the data cut-off for the analysis and patients who completed the study will be censored at study completion. The standard errors (SEs) will be computed using the Greenwood's formula, the CI for the median will be calculated according to Brookmeyer and Crowley (1982), and the CIs for the survival function estimates at above mentioned time points will be derived from the Kaplan-Meier estimates using the log-log transformation

Number of patients included and excluded from each analysis set (including reason for exclusion) will be summarized overall and by treatment arm based on the FAS. The control arm of a candidate agent (refer to Section 4.5) will be further broken down by sub-protocol.

Listings for randomization schemes/codes and disposition data will be provided separately.

9.1.1. DERIVATIONS

- Time to discontinuation from study (days) = (Date of study discontinuation – Date of Study Day 1 [refer to Section 6.1]) + 1

Date of study discontinuation will be captured on the *Disposition* page of the eCRF.

Patients who are ongoing in the study at the time of an analysis will be censored at the date of the last contact before or on the date of the data cut-off for the analysis and patients who completed the study will be censored at study completion.

9.2. PROTOCOL DEVIATIONS

All protocol deviations (critical, major, and minor) will be recorded in the clinical trial management system (CTMS) protocol deviations log for the duration of the study (refer to the Protocol Deviations Management Plan for the definition of critical, major, and minor protocol deviations). Site-level identified protocol deviations will be replicated for all patients ongoing in the study at the site at the time of the protocol deviation and presented in the summary outputs as patient-level protocol deviation.

Number and percentage of patients with critical and major protocol deviations will be provided overall and by treatment arm based on the FAS for each category of protocol deviations specified in the Protocol Deviations Management Plan. The control arm of a candidate agent (refer to Section 4.5) will be further broken down by sub-protocol.

A listing of all protocol deviations (critical, major, and minor) will be provided.

10. DEMOGRAPHIC AND OTHER BASELINE CHARACTERISTICS

The following demographic and other baseline characteristics will be reported for this study:

[figure not shown]
- Age (years) – in integers, calculated relative to date of consent:
 - As a continuous variable;
 - As a categorical variable ($\geq 18 - \leq 49$, $\geq 50 - \leq 64$, $\geq 65 - \leq 84$, or ≥ 85);
- Sex (male or female);

CCI

PPD

Version Number: Amendment 1, v1.0
Version Date: 23Apr2021

CCI

- Childbearing potential for female patients only (yes or no) and reasons if not of childbearing potential;
- Race:
 - American Indian or Alaska Native, Asian, Black or African American, Native Hawaiian or Other Pacific Islanders, White, multiple, not reported, or unknown;
 - White, Black or African American, others, not reported, or unknown;
- Ethnicity (Hispanic or Latino, not Hispanic or Latino, not reported, or unknown);
- Country;
- Region (if applicable, refer to Section 7.5);
- Height (cm);
- Weight (kg);
- Body Mass Index (BMI) (kg/m²);

Demographic and other baseline characteristics will be summarized overall and by treatment arm based on the FAS. The control arm of a candidate agent (refer to Section 4.5) will be further broken down by sub-protocol. No statistical testing will be carried out for any demographic or other baseline characteristic.

Demographic and other baseline characteristics data will be listed.

